3.1. Background

Portal hypertension is high blood pressure in the portal vein located in the abdomen. The portal vein returns blood from the digestive system to the liver for the purpose of cleaning and filtering waste from the blood. This condition is the most frequent cause of hospitalization, variceal bleed, liver transplantation, and death in patients with cirrhosis.¹

Elevated pressures in the portal venous system will manifest as abdominal ascites, hepatic hydrothorax, hepatorenal syndrome, portal hypertensive gastropathy and gastro-esophageal varices with or without bleeding, which are markers of decompensation and associated with significant morbidity and mortality.

Transjugular intrahepatic portosystemic shunt (TIPS) is a well-established percutaneous modality for decreasing portal hypertension by creating a shunt through the hepatic parenchyma to connect the hepatic vein to the portal vein. Although the major clinical indications for TIPS include refractory variceal hemorrhage and refractory ascites, the full list of TIPS indications includes:²

1. Uncontrollable variceal hemorrhage
2. Current or prior variceal hemorrhage that is not amenable to initial or continued endoscopic therapy
3. Prophylaxis against recurrent variceal bleed in high-risk patients
4. Portal hypertensive gastropathy
5. Refractory ascites
6. Hepatic hydrothorax
7. Budd-Chiari syndrome
8. Hepatopulmonary syndrome
9. Hepatorenal syndrome
10. Decompression of portosystemic collaterals prior to abdominal surgical procedures

Overall, the TIPS procedure is one of the most challenging procedures performed by interventional radiologists, and the most difficult and time-consuming step in the procedure is accessing the portal vein. Many techniques for accessing the portal vein have been described in literature and they fall into three broad categories:

- Fluoroscopically guided TIPS creation with the use of landmarks or portography (wedged hepatic vein portography with CO₂ umbilical venography)
- Transabdominal ultrasound – guided placement of a portal vein target via transhepatic or transsplenic access to facilitate subsequent fluoroscopically guided access

- Transabdominal intravascular ultrasound (IVUS), or intracardiac echocardiography (ICE) guidance³

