ICE uses a low-frequency, side-firing intravascular transducer and is more commonly used for intracardiac procedures. However, in this application it can be used to depict the central portion of the liver, which permits visualization of the needle and the PV target without the use of fluoroscopy or contrast medium.

Cam et al.⁴ reported that ultrasound-guided PV access and percutaneous PV guidewire placement for fluoroscopic targeting during TIPS creation are associated with shorter procedure and fluoroscopic times and potentially decreased complications. Many of the procedure-related complications of TIPS creation, such as arterial injury, biliary injury, and extracapsular puncture may occur during attempted portal vein access. As the number of needle passes for successful PV access increases, so may the potential for puncture-related complications.

Historically, the most performed technique for portal venous access involved wedge hepatic venography with carbon dioxide to visualize the portal vein followed by passing the needle under fluoroscopic guidance. In the last 10 years, imaging guidance options have evolved beyond traditional wedge carbon dioxide portography to include ultrasound-guided options such as transabdominal, intravascular and intracardiac echocardiography to help with visualization and portal vein cannulation. Portal vein access may require multiple needle passes and is considered the riskiest step in TIPS creation with possible incidence of portal vein puncture-related complications (PVPC).⁵ Complications result from inadvertent injury to non-target vessels and include damage to the hepatic artery or extrahepatic portal vein, transcapsular puncture and laceration of the liver capsule, all of which can result in life-threatening hemorrhage.⁶

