3.2. Prior Investigations

The Rosch-Uchida and Colapinto sets manufactured by Cook Medical (Bloomington, Indiana, US) are two different needle sets currently available and most encountered. A recent systematic review of literature showed that the overall incidence of PVPC with the Cook sets was 3.6%.⁶ The procedure duration varies in literature due to protocol differences and imaging techniques used. David et al.⁷ reported a mean procedure duration of 86.2 minutes using ultrasound guidance. In a study evaluating time to portal vein access, mean time to portal venous access was statistically significant between conventional fluoroscopy at 46 minutes and intravascular US-guided TIPS at 31 minutes.⁸

In the paucity of studies available which focus on portal vein access in TIPS interventions, there are few that demonstrate significant differences between the number of needle passes. The data is incomplete because fewer than half of conventional TIPS cases in literature included a recording of the actual number of passes. The Scorpion devices allow for bi-directional positioning of the needle or stylet for precise placement during portal vein puncture.

In a retrospective study of 15 cases with Scorpion X (Needle model), technical success was achieved in 100% of cases with an average of 2.7 passes, and because of the bi-directional needle, no cases required adjustment to the curvature of the needle.⁹

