11.3.2. Primary Effectiveness Set

The primary effectiveness set will include procedures/patients who have a successful procedure with only a study device (i.e., no need of an alternative device).

This set will be the base for assessment of cannulation time, fluoroscopy time, procedure duration, as well as other device-specific outcomes.

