11.3.3. Safety Population

Safety set will include all procedures/patients defined in the intent-to-treat set.

This set will be the base for the overall study safety assessment.

For study device-specific post-operation safety assessment, only those included in the primary effectiveness set will be used.

Comparability analyses between the two study groups will be conducted on the Intent-to-Treat analysis set.

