11.5. Interim Analysis

One interim analysis will be conducted when the first 15 cases in each group complete the study procedure. The main purpose of the interim analysis is to more accurately fine tune the study design based on study-specific data. The interim analysis will focus on the impact of the primary imaging techniques on procedural success. If imaging technique is a significant factor, stratified randomization by primary imaging techniques will apply for future included participants. Justification for multiplicity is unnecessary as no formal statistical hypothesis will be tested.

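### Imaging technique is neither recorded before randomisation nor named as a covariate for the time endpoints; the only safeguard is an undefined significance trigger at half enrolment

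*Combined protocol and SAP*

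**What the plan says.** Section 11.5 plans one interim look when 15 cases per group have completed the procedure. On its content it says "The interim analysis will focus on the impact of the primary imaging techniques on procedural success", and on its consequence "If imaging technique is a significant factor, stratified randomization by primary imaging techniques will apply for future included participants". It gives no test, significance level, effect threshold or list of imaging categories. Section 3.1 says of portal vein access techniques that "they fall into three broad categories", but nothing maps these to strata. Section 7.7 describes central 1:1 allocation and names no stratification factor. Section 13.10 lists stratification among the measures against bias, on condition that the interim triggers it.

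The evidence the protocol cites on imaging is mainly about time. Section 3.1 reports that ultrasound-guided access and percutaneous wire targeting "are associated with shorter procedure and fluoroscopic times and potentially decreased complications". Section 3.2 gives the only numerical contrast between imaging techniques: "mean time to portal venous access was statistically significant between conventional fluoroscopy at 46 minutes and intravascular US-guided TIPS at 31 minutes".

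Section 11.1.2 compares groups by Student's t-test or Pearson's chi-square. It allows unbalanced baseline variables to be explored, mixed models where needed, and subgroup results by type of image if numbers permit. Imaging is not named as a covariate. Section 8.3 lists the imaging used among the data recorded at the procedure, and the screening data in section 8.2 include no planned guidance technique.

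On analysis sets, section 11.3.2 states "The primary effectiveness set will include procedures/patients who have a successful procedure with only a study device" and "This set will be the base for assessment of cannulation time, fluoroscopy time, procedure duration, as well as other device-specific outcomes". Section 11.3.3 adds "Comparability analyses between the two study groups will be conducted on the Intent-to-Treat analysis set".

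**The concern.** If imaging guidance shifts access time by something like the cited 15 min, a chance difference in imaging mix between two arms of 30 adds noise to every time comparison. The plan's response is a significance test on a different, binary endpoint where few failures are likely, applied once half the subjects have been allocated. Because no test or categories are stated, two statisticians with the same 30 cases could reach opposite decisions.

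Even a positive decision could not be carried out as written, because no imaging variable exists before randomisation to stratify on. For the same reason there is no clean covariate for the analysis. What is at stake is precision in the exploratory comparisons of portal vein access (PVA) time, fluoroscopy time and procedure duration. Section 3.3 says the study will supply clinical data for a CE Mark application and preliminary performance data against competitor devices.

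**Working it through.** **Inputs from the documents.** Interim at 15 per group, so 30 cases (11.5). Planned total 60, 30 per group (6.6). Access time 46 vs 31 min (3.2), a difference of 46 − 31 = 15 min.

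**Assumptions, because the documents give no figure.** Trigger at two-sided 0.05, by uncorrected Pearson or Fisher. Failure 20% with one technique and 5% with the other, with 20% vs 0% as an alternative. Two imaging groups split 15:15, 20:10 or 24:6. Within-technique SD of access time 15 to 30 min, normal errors. Imaging mix 50:50 or 80:20.

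The plan states no operating figure for the trigger, so there is none to reproduce.

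**Step 1: failures needed at 15:15.** With k failures in one imaging group and none in the other, Pearson X² = 30·(15k)² / [15·15·k·(30 − k)].
- k = 3: 60,750 / 18,225 = 3.33, p = 0.068. Does not fire.
- k = 4: 108,000 / 23,400 = 4.62, p = 0.032. Fires; Fisher gives p = 0.0996 and does not.
- k = 5: Fisher p = 0.042. Both fire.

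So four failures against none triggers stratification under one test and not the other. At 95% overall success, 30 × 0.05 = 1.5 failures are expected in total.

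**Step 2: chance that the trigger fires.** Sum the product of the two binomial probabilities over all outcomes with p < 0.05.

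| Split | Failure rates | Pearson | Fisher |
|---|---|---|---|
| 15:15 | 5% vs 20% | 18.8% | 8.3% |
| 24:6 | less-used technique 20%, other 5% | 37.4% | 16.1% |
| 24:6 | more-used technique 20%, other 5% | 0.55% | 0.06% |
| 15:15 | 0% vs 20% | 35% | 16% |
| 20:10 | less-used technique 20%, other 0% | 62% | 32% |
| 24:6 | less-used technique 20%, other 0% | 74% | 34% |

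**Step 3: timing.** 30/60 = 50% are already randomised at the earliest possible switch. No enrolment pause is stated, so the share could be higher.

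**Step 4: what each remedy does for PVA time.** These figures take all 60 subjects with none excluded. Let s be the within-technique SD and p the share using one technique.
- Unadjusted t-test: SE = √[2(s² + 15²·p(1 − p))/30]. At p = 0.5, s = 15: √[2(225 + 56.25)/30] = 4.33. At p = 0.8, s = 15: √[2(225 + 36)/30] = 4.17. At s = 30: √[2(900 + 56.25)/30] = 7.98 and √[2(900 + 36)/30] = 7.90.
- With imaging as a covariate, the between-technique term drops out: SE is close to s√(2/30), which is 3.87 at s = 15 and 7.75 at s = 30, plus a small penalty for chance imbalance.

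Simulated mean reported SE at a 50:50 mix (permuted blocks of 4):

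| Design and analysis | s = 15 | s = 30 |
|---|---|---|
| Unstratified, t-test | 4.31 | 7.95 |
| Stratified from the start, t-test | 4.32 | 7.96 |
| Unstratified, covariate | 3.89 | 7.78 |
| Stratified from the start, covariate | 3.86 | 7.72 |

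- Covariate alone, 50:50: 1 − 3.89/4.31 = 9.7% at s = 15; 1 − 7.78/7.95 = 2.1% at s = 30.
- Covariate alone, 80:20, s = 15: simulated SE 3.89 against 4.15 unadjusted, 1 − 3.89/4.15 = 6.3%. At s = 30 the gain is between 1% and 2%.
- Stratification on top of the covariate: 1 − 3.86/3.89 = 0.8%; 1 − 7.72/7.78 = 0.8%.
- Stratification with the t-test: the true sampling SD of the difference falls (4.32 to 3.89 at 50:50, s = 15), but the reported SE does not move, because the pooled SD still contains the between-technique variance. The test becomes conservative and the interval is no narrower.

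**The case against.** The strongest reply is that little depends on this. Sections 6.2 and 11.2 test no hypothesis and call the sample size empirical, and unstratified 1:1 allocation is unbiased. Firing by mistake does no harm, since it only produces stratification. Procedural success is the primary effectiveness endpoint, so looking at it first is defensible. Section 11.1.2 also gives imaging an explicit place through subgroup results by image type, and leaves room for modelling. All of this stands and keeps the point modest. But subgroup reporting if numbers permit is not adjustment, and the modelling is conditional and does not name imaging.

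Four stronger readings are tempting and are not supported:
- A reader might infer that the trigger will almost never fire. That depends on test and split: Pearson exceeds 50% at 20% vs 0% failure when the less-used technique is the worse one.
- A reader might infer that stratification is the main remedy. Step 4 shows that it leaves the reported t-test interval unchanged and adds little once a covariate is used.
- A reader might infer that imaging imbalance goes unchecked in the Primary Effectiveness Set because comparability is assessed on the Intent-to-Treat set. The text does not show imaging to be part of that check in any set: section 11.1.2 bases it on demographic and clinical parameters, and section 8.3 treats imaging as procedure data.
- A reader might infer bias in the device comparison from missing stratification. Randomisation rules that out among all randomised subjects.

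**Conclusion.** The point holds as a modest one, worth considering. The stratification rule is undefined, its chance of acting runs from under 1% to about 74% across the assumed scenarios, and it acts after at least half the sample. The more consequential gap is that no planned-imaging variable is captured before assignment and none is prespecified as a covariate, although the protocol's own figures suggest that imaging affects access time.

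If the 15 min difference applies, the avoidable loss is about 10% of the standard error (50:50 mix) or 6% (80:20) at a within-technique SD of 15 min, and 1-2% at 30 min. These are upper bounds, because planned imaging may differ from imaging used. They also rest on assumed SDs and mixes, and on all 60 subjects contributing. The 15 min figure is for access time; the documents give no comparable figure for fluoroscopy time or procedure duration.

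No formal conclusion fails. Neither remedy cures the selection in the Primary Effectiveness Set, which is formed after randomisation from procedures that succeeded without an alternative device.

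**What to change.** **Main change.** Define two or three imaging categories, record the planned primary imaging technique before randomisation, and prespecify it as a covariate for PVA time, fluoroscopy time and procedure duration in section 11.1.2.

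**Secondary change.** Drop the significance trigger in section 11.5 and stratify the central randomisation by planned imaging from the first subject, or from now on if enrolment has begun. Pair this with the adjusted analysis; without it the reported interval does not narrow.

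**Reporting.** Describe imaging actually used by arm, but do not adjust for it: it is recorded at an open-label procedure and can follow device assignment. Update section 13.10 to match.

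**Cost.** One extra field, and a declaration of technique before assignment, which stratifying after the interim would need in any case. If enrolment has begun, an amendment with IRB approval under section 12.6.1 is likely to be needed at up to six sites. In that case only the covariate may be worth adding, for subjects whose planned technique was documented before assignment.

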11.1.2. Exploratory Comparisons

Between-group comparisons will be conducted using Student's t-test for continuous variables and Pearson's Chi-square test for categorical variables. Comparability analysis between two study groups will be first conducted based on demographic and clinical parameters.

Appropriate statistical methods will be employed to explore the correlation and impact of the unbalanced baseline variable, if any, on the study results. When necessary, advanced statistical method such as mixed linear models will be employed to justify the impact.

When sample size permits, the outcomes will be reported for sub-groups such as by gender, age group (≤ 50 years vs > 50 years), type of image used, or operation experience.

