13.10. Minimization of Bias

The following activities are intended to reduce the risk of bias:

- Randomized study
- Objective methodology to evaluate endpoints
- Stratified randomization (if applicable after the interim analysis)

Furthermore, potential for bias has been minimized with a well-controlled design, expected conduct under the terms of the approved protocol, use of specific inclusion and exclusion criteria, careful definitions for study procedures and outcomes, and prospectively defined methods of data analysis.

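### If the interim triggers stratified randomisation by imaging, the named tests stay unstratified: mildly conservative for time outcomes, immaterial for procedural success

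*Combined protocol and SAP*

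**What the plan says.** Section 11.5 plans one interim look, "when the first 15 cases in each group complete the study procedure", that is after 30 of the 60 planned subjects. It examines how primary imaging technique affects procedural success. The trigger reads "If imaging technique is a significant factor", with no test, level or threshold attached. If it is met, "stratified randomization by primary imaging techniques will apply for future included participants". Section 13.10 counts this possible stratification among the measures against bias.

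Section 11.1.2 sets the comparative analysis: "Between-group comparisons will be conducted using Student's t-test for continuous variables and Pearson's Chi-square test for categorical variables". On adjustment it says: "Appropriate statistical methods will be employed to explore the correlation and impact of the unbalanced baseline variable, if any, on the study results". It adds mixed linear models for use where they are judged necessary. Imaging type is otherwise named only as a possible subgroup, if numbers allow.

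Section 11.3.2 places cannulation time, fluoroscopy time and procedure duration in the primary effectiveness set, meaning procedures that succeeded with the study device alone. Section 8.3 lists the imaging used among the procedure data to be collected.

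**The concern.** A factor used to restrict the randomisation normally enters the analysis. Stratifying by a prognostic factor reduces the variance of the treatment difference, but a plain t-test still counts the whole between-technique variation in its standard error. The test then reports more uncertainty than the design leaves.

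The adjustment clause does not close the gap. It depends on imbalance being found, and stratification makes imbalance in imaging less likely. Section 11.6 also requires analyses not identified in the protocol to be flagged in the report, so an imaging-adjusted comparison added later could carry that label.

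At stake is some precision on the time-based secondary endpoints of a 60-subject study whose data are also meant for a CE mark application (Sections 3 and 3.3).

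**Working it through.** **The plan's own figure.** The sample size of 60 (30 per group) is called empirical in Section 11.2. It has no power, effect size or SD behind it, so there is nothing to reproduce.

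**Inputs from the documents.** N = 60, allocation 1:1, the first 30 unstratified and at most the last 30 stratified (Sections 6.6, 7.7, 11.5). Section 3.2 gives mean access time as "conventional fluoroscopy at 46 minutes and intravascular US-guided TIPS at 31 minutes", a gap D = 46 − 31 = 15 minutes.

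**Assumptions, not in the documents.** Two imaging techniques, one with share p = 0.5; within-technique SD σ of 12 to 25 minutes; permuted blocks of 4; two-sided 5% level; a 10-minute device difference for power.

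**Closed form.** The between-technique variance is B = p(1 − p)D² = 0.25 × 225 = 56.25.

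- SE used by the t-test: √[(σ² + B) × 2/30].
- True SD of the difference with half the sample perfectly balanced: √[(σ² + B/2) × 2/30], because B is removed from one half only.
- SE with imaging in the model: √[σ² × 2/30].

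For σ = 12 these are √(200.25/15) = 3.65, √(172.125/15) = 3.39 and √(144/15) = 3.10 minutes. The t-test's SE is 3.65/3.39 = 1.08 times the true SD. For σ = 25 they are √(681.25/15) = 6.74, √(653.125/15) = 6.60 and √(625/15) = 6.45, a ratio of 1.02. Incomplete blocks leave the balance imperfect, so these ratios are upper limits.

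**Simulation, 20,000 trials per setting:**

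| σ (min) | True SD of difference | Mean t-test SE | Ratio | Type I error, t-test | Type I error, imaging adjusted | Power, t-test | Power, strata as randomised | Power, imaging adjusted in all |
|---|---|---|---|---|---|---|---|---|
| 12 | 3.41 | 3.65 | 1.07 | 3.7% | 5.1% | 78% | 82% | 89% |
| 15 | 4.15 | 4.31 | 1.04 | 3.8% | 5.1% | 62% | 66% | 71% |
| 20 | 5.35 | 5.50 | 1.03 | 4.3% | 5.0% | 43% | 45% | 47% |
| 25 | 6.67 | 6.71 | 1.01 | 4.8% | 5.2% | 30% | 31% | 33% |

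In the column for strata as randomised, the first 30 subjects form one stratum.

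**Imaging mix.** With p = 0.1, B = 0.09 × 225 = 20.25. The upper-limit ratio at σ = 12 is √(164.25/154.125) = 1.03, and at σ = 25 it is √(645.25/635.125) = 1.01.

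**How much is lost.** In a smaller run (4,000 trials, σ = 12), the true SD of the unadjusted difference falls from 3.68 minutes without stratification to 3.46 with half the sample stratified. That gain in balance survives the plain t-test. In the same run, the ratio of unadjusted to adjusted interval width is 1.17 without stratification and 1.18 with it. Most of the power gain therefore comes from adjusting for imaging at all.

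**Procedural success (10,000 trials, half stratified, assumed 20-point device difference):**

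| Assumed success by technique | Unadjusted SE ÷ true SD | Power, chi-square | Power, Cochran-Mantel-Haenszel |
|---|---|---|---|
| 95% / 100% | 0.98 | 73% | 72% |
| 90% / 98% | 0.99 | 59% | 58% |
| 80% / 95% | 0.99 | 46% | 47% |
| 70% / 95% | 1.01 | 42% | 44% |

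There is no material loss on the binary primary endpoint.

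**Chance of the trigger.** Taking 15 subjects per technique and a chi-square test at 5% (assumed, since the plan names no rule), the trigger fires with probability 0.5%, 4%, 19% and 44% in the same four scenarios.

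**The case against.** The strongest reply is that little turns on this. The comparisons are exploratory and no hypothesis is tested. The error is conservative, so it adds no false positives. The trigger may well not fire. Section 11.1.2 also leaves a route to adjusted models, and with the first 30 subjects unstratified some imbalance can still arise. In a simulation with a 50:50 mix, the arms differed by 10 points or more on imaging in 27% of trials. The SD and imaging mix are assumed, and the 15-minute gap comes from a single cited comparison. The time outcomes are analysed in the primary effectiveness set, so fewer than 60 subjects may contribute.

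All of this stands and limits the size of the point. It does not remove it: the adjustment route is discretionary and tied to observed imbalance, not to the stratification factor.

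A reader might infer three stronger things that the documents do not support:

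- That the benefit of stratifying is thrown away. It stays in the point estimate; only its reflection in the standard error and p-value is lost.
- That planned confidence intervals will be too wide. Section 11.1.1 names none, so the excess lies in the standard error inside the test.
- That the primary effectiveness comparison is compromised. The figures for procedural success show no material effect.

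**Conclusion.** The point holds as a minor specification gap. If stratification is triggered, the plan has no rule for carrying imaging into the between-group comparison, and the named t-test is mildly conservative for continuous outcomes that imaging affects. Under the stated assumptions the standard error is about 1 to 7% too large and type I error about 3.7 to 4.8%, less if one technique is rare. Modelling imaging in all subjects raises power for an assumed 10-minute difference from 62% to 71% at an SD of 15, and from 30% to 33% at an SD of 25. Much of that is ordinary covariate adjustment and should not be read as the cost of the mismatch. The calculation uses access time, the only outcome for which the documents give an imaging gap. Extending it to fluoroscopy time and procedure duration assumes that imaging affects them similarly.

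**What to change.** Add to Section 11.1.2: if stratified randomisation is triggered under Section 11.5, between-group comparisons of continuous outcomes use a linear model with arm, primary imaging technique for all subjects, and an indicator for enrolment before or after the interim, in the analysis set defined for that outcome. The unadjusted t-test is reported as a sensitivity analysis.

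For stratified subjects, use the planned technique recorded at randomisation. For earlier subjects, use the imaging already collected under Section 8.3. That record is made at an open-label procedure after allocation, so the report should say so.

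For binary outcomes, a Cochran-Mantel-Haenszel analysis would match the design but brings no material gain in precision.

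The cost is one sentence and a few degrees of freedom. No new outcome data and no added patient burden are involved; the planned technique has to be entered at randomisation for stratification in any case.
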